4.3. Exclusion Criteria

Subjects who meet *any* of the following exclusion criteria are not to be enrolled in this study.

- 1) Co-infection with HIV, acute hepatitis A virus (HAV) infection or chronic HBV coinfection (HBsAg positive [HBsAg+] at screening)
- 2) Decompensated liver disease defined as INR > 1.2 x ULN, platelets < 50,000/mm³, serum albumin < 3.0 g/dL, or prior history of clinical hepatic decompensation (eg, ascites, jaundice, encephalopathy, variceal hemorrhage)
- 3) Evidence of a gastrointestinal malabsorption syndrome that may interfere with absorption of orally administered medications
- 4) Chronic liver disease of non-HCV etiology (eg, hemochromatosis, Wilson's disease, alpha-1 antitrypsin deficiency)
- 5) Evidence of hepatocellular carcinoma (HCC) or other non-hematologic malignancy (with the exception of certain resolved skin cancers)

Note: liver imaging within 6 months of baseline/Day 1 is required in patients with cirrhosis to exclude HCC

- 6) History of solid organ or bone marrow transplantation
- 7) Active or recent history (\leq 1 year) of alcohol or drug abuse
- 8) Serum creatinine > 1.5 mg/dL
- 9) Estimated glomerular filtration rate < 90 mL/min/1.73m², as calculated by the Schwartz formula
- 10) Investigational agents taken within the past 28 days (except with the prior written approval of the Sponsor)
- 11) Use of any prohibited concomitant medications as described in Section 5.3
- 12) Pregnant or lactating subjects
- 13) Sexually-active males or females of childbearing potential who are not willing to use an effective method of contraception during the study (see [Appendix 4](#) for further details)
- 14) Unable to swallow the LDV/SOF FDC 90mg/400mg and the LDV/SOF FDC 22.5mg/100mg placebo tablets
- 15) Known hypersensitivity to LDV, SOF, metabolites, or formulation excipients
- 16) Subject unable to comply with the dosing instructions for study drug administration and/or unable to complete the study schedule of assessments

5. INVESTIGATIONAL MEDICINAL PRODUCTS

5.1. Description and Handling of LDV/SOF FDC

5.1.1. Formulation

LDV/SOF FDC tablets are orange, diamond-shaped, film-coated tablets containing 90 mg of LDV and 400 mg of SOF. The tablets are debossed with “GSI” on one side and “7985” on the other side. The SOF/LDV FDC tablets contain the following inactive ingredients: lactose monohydrate, copovidone, microcrystalline cellulose, croscarmellose sodium, colloidal silicon dioxide, magnesium stearate, polyvinyl alcohol, titanium dioxide, talc, polyethylene glycol, FD&C yellow # 6 /sunset yellow FCF Aluminium Lake.

Placebo to match LDV/SOF FDC 90 mg/ 400 mg tablets for Swallowability Assessment are orange, diamond-shaped, film-coated tablets debossed with “GSI” on one side and “7985” on the other side. The tablets contain lactose monohydrate, copovidone, microcrystalline cellulose, croscarmellose sodium, magnesium stearate, polyvinyl alcohol, titanium dioxide, talc, polyethylene glycol, FD&C yellow # 6 /sunset yellow FCF aluminum lake.

Age-appropriate formulations of LDV/SOF FDC have been developed for subjects who are unable to swallow the LDV/SOF FDC 90 mg/ 400 mg tablets which include a lower dose strength tablet (LDV/SOF FDC 22.5 mg/ 100 mg) formulation. LDV/ SOF FDC lower dose strength tablets are round, plain-faced, white film-coated tablets containing 22.5 mg of LDV and 100 mg of SOF. The LDV/SOF FDC lower dose strength tablets contain the following inactive ingredients: lactose monohydrate, copovidone, microcrystalline cellulose, croscarmellose sodium, colloidal silicon dioxide, magnesium stearate, polyvinyl alcohol, titanium dioxide, talc and polyethylene glycol.

Placebos to match LDV/SOF FDC 22.5 mg/ 100 mg tablets for Swallowability Assessment are round, plain-faced, white film-coated tablets. The placebo tablets contain the following inactive ingredients: lactose monohydrate, copovidone, microcrystalline cellulose, croscarmellose sodium, magnesium stearate, polyvinyl alcohol, titanium dioxide, talc and polyethylene glycol.

5.1.2. Packaging and Labeling

LDV/SOF FDC tablets are packaged in white, high density polyethylene (HDPE) bottles. Each bottle contains 28 or 30 tablets, silica gel desiccant and polyester packing material. Each bottle is enclosed with a white, continuous thread, child-resistant screw cap with an induction-sealed, aluminum-faced liner.

Placebo tablets to match LDV/SOF FDC 90 mg/ 400 mg tablets for Swallowability Assessment are packaged in white, high density polyethylene (HDPE) bottles. Each bottle contains 28 or 30 tablets, a silica gel desiccant and polyester packing material. Each bottle is enclosed with a white, continuous thread, child resistant screw cap with an induction-sealed, aluminum faced liner.

LDV/SOF FDC 22.5 mg/ 100 mg tablets are packaged in white, high density polyethylene (HDPE) bottles. Each bottle contains 28 or 30 tablets, a silica gel desiccant, and polyester packing material. Each bottle is enclosed with a white, continuous thread, child resistant screw cap with an induction-sealed, aluminum faced liner.

Placebo tablets to match LDV/SOF FDC 22.5 mg/ 100 mg tablets for Swallowability Assessment are packaged in white, high density polyethylene (HDPE) bottles. Each bottle contains 28 or 30 tablets, a silica gel desiccant and polyester packing material. Each bottle is enclosed with a white, continuous thread, child resistant screw cap with an induction-sealed, aluminum faced liner.

All LDV/SOF FDC and placebo to match LDV/SOF FDC bottles to be distributed to centers shall be labeled to meet all applicable requirements of the US Food and Drug Administration (FDA), Annex 13 of Good Manufacturing Practices: Manufacture of investigational medicinal products (Feb 2010) and/or other local regulations as applicable.

5.1.3. Storage and Handling

LDV/SOF FDC tablets (both 90 mg/400 mg and 22.5 mg/100 mg strength) and placebo to match LDV/SOF FDC tablets (for both both 90 mg/400 mg and 22.5 mg/100 mg strengths), for Swallowability Assessment should be stored at controlled room temperature until required for administration. Controlled room temperature is defined as 25 °C (77 °F); excursions are permitted between 15 °C and 30 °C (59 °F to 86 °F).

All drug products should be stored in a securely locked area, accessible only to authorized site personnel. To ensure the stability of the study drug and to ensure proper product identification, the drug product should not be stored in a container other than the container in which they are supplied. Consideration should be given to handling, preparation, and disposal through measures that minimize drug contact with the body. Appropriate precautions should be followed to avoid direct eye contact or exposure through inhalation when handling LDV/SOF FDC.

Sufficient quantities of LDV/SOF FDC tablets and placebo tablets will be shipped to the investigator or qualified designee from Gilead Sciences (or its designee).

5.2. Dosage and Administration of LDV/SOF FDC

LDV/SOF FDC 90 mg/ 400 mg tablet is to be administered once daily with or without food. Subjects determined unable to swallow the placebo to match the 90 mg/400 mg LDV/SOF FDC tablet (by LDV/SOF FDC Placebo Swallowability Assessment at Screening up to Day 1) will be re-assigned to 4 x 22.5 mg/ 100 mg tablets daily. Each subject must be given instructions to maintain approximately the same daily dosing interval between study drug doses. In order to maintain compliance with the treatment regimen, LDV/SOF FDC should be administered at approximately the same time each day.

For a missed dose of LDV/SOF FDC tablet, subjects should be instructed to take the missed dose of study drug as soon as possible during the same day. Subjects should be cautioned never to double the next dose with a missed dose of study drug under any circumstances.

5.3. Prior and Concomitant Medications

Concomitant medications taken within 30 days prior to screening, up to and including 30 days after the last dose of study drug need to be recorded in the source documents and electronic case report form(s) (eCRFs).

Investigational agents or devices for any indication are prohibited during the screening period and for a minimum of 28 days prior to the Baseline/Day 1 visit through the end of treatment.

Concomitant use of certain medications or herbal/natural supplements (inhibitors or inducers of drug transporters ie, P-gp) with study drug(s) may result in PK interactions resulting in increases or decreases in exposure of study drug(s). Examples of representative medications which are prohibited from **21 days prior to Baseline/Day 1** through the end of treatment are listed below. The use of amiodarone is prohibited from **60 days prior to Baseline/Day 1** through the end of treatment:

Table 5-1. Disallowed and Concomitant Medications to be Used with Caution

Drug Class	Agents Disallowed	Use with Caution
Acid Reducing Agents ^a		Proton- Pump Inhibitors, H2-Receptor Antagonists, Antacids
Anticonvulsants ^b	Phenobarbital, Phenytoin, Carbamazepine, Oxcarbazepine	
Antimycobacterials ^b	Rifabutin, Rifapentine, Rifampin	
Cardiac Medications	Amiodarone ^c	Digoxin ^d
Herbal/Natural Supplements ^b	St. John's Wort, Echinacea, Milk thistle (i.e., silymarin), Chinese herb sho-saiko-to (or Xiao-Shai-Hu-Tang)	
HMG-CoA Reductase Inhibitors ^e	Rosuvastatin	

- a It is recommended to separate antacid and LDV/SOF administration by 4 hours. H2-receptor antagonists may be administered simultaneously with or staggered from LDV/SOF at a dose that does not exceed doses comparable to famotidine 40 mg twice daily. Proton-pump inhibitor doses comparable to omeprazole 20 mg can be administered simultaneously with LDV/SOF. Proton-pump inhibitors should not be taken before LDV/SOF.
- b May result in a decrease in the concentrations of study drug.
- c May result in symptomatic bradycardia. Mechanism is not currently known. The use of amiodarone is prohibited from **60 days prior to Baseline/Day 1** through the end of treatment.
- d May result in an increase in the concentration of study drug and/or concomitant medications. Co-administration of LDV/SOF with digoxin may increase the concentration of digoxin. Caution is warranted and therapeutic concentration monitoring of digoxin is recommended when co-administered with LDV/SOF.
- e Use with study drug may result in an increase in the concentration of rosuvastatin. Monitor for signs and symptoms of muscle weakness or myopathy, including rhabdomyolysis.

Medications for disease conditions **excluded** from the protocol (e.g., active cancer [other than hematological malignancy], transplantation) are not listed under this Concomitant Medication section and are disallowed in the study.

5.3.1. Allowed Maintenance Chemotherapy Medications

Acceptable maintenance chemotherapy medications allowed in this study include the following:

- Vincristine
- Methotrexate
- 6-mercaptopurine (6-MP)

L-asparaginase and aracytine and/or short courses of steroids such as prednisone may also be used.

Administration of these medications should be staggered relative to dosing of LDV/SOF to minimize any potential for drug-drug interactions. For example, if subjects receive their maintenance chemotherapy in the morning, LDV/SOF should be taken in the evening.

Additional chemotherapy medications may be used after review and agreement by Gilead.

5.4. Accountability for LDV/SOF FDC

The investigator is responsible for ensuring adequate accountability of all used and unused study drug. This includes acknowledgement of receipt of each shipment of IMP (quantity and condition). All used and unused study drug dispensed to subjects must be returned to the site.

LDV/SOF FDC accountability records will be provided to each study site to:

- Record the date received and quantity of study drug kits
- Record the date, subject number, subject initials, the study drug kit number dispensed
- Record the date, quantity of used and unused study drug returned, along with the initials of the person recording the information.

Subjects must be instructed to bring back all study drug in the original container at every post-Day 1 study visit through the end of treatment.

5.4.1. Investigational Medicinal Product Return or Disposal

Please refer to Section [9.1.7](#) for Investigational Medicinal Product Accountability and Return.

6. STUDY PROCEDURES

The study procedures to be conducted for each subject enrolled in the study are presented in tabular form in [Appendix 2](#) and described in the text that follows. Additional information is provided in the study procedures manual.

The investigator must document any deviation from protocol procedures and notify the sponsor or contract research organization (CRO).

6.1. Subject Enrollment and Treatment Assignment

6.1.1. Screening Visit

Subjects will be screened within 28 days of Day 1 to determine eligibility for participation in the study. The screening window can be extended to 42 days prior to Day 1 in extenuating circumstances with sponsor approval.

The following assessments will be done at screening:

- Obtain parent or guardian consent and assent from the child; written assent should be provided if applicable
- Collect medical history, demographics, and concomitant medications
- Ask subject and/or parent/legal guardian if the subject is able to swallow and tolerate taking pills.
- Perform LDV/SOF FDC swallowability assessment
- Perform physical exam (PE) including vital signs (VS), body weight, and height
- Collect blood samples for
 - HCV antibody, HAV antibody, HIV antibody, HBsAg, HBsAb, HBcAb
 - HCV RNA
 - HCV genotype
 - Clinical chemistry (including Fibrotest), hematology (including APRI calculation) , and coagulation
 - Pregnancy test (females of childbearing potential only)
- Fibrosis assessment with Fibroscan; liver biopsy may be done if required

— For patients with cirrhosis, diagnostic imaging (CT or ultrasound) if results not available from imaging done within 6 months of Day 1 that excludes the presence of hepatocellular carcinoma (HCC)

- Collect urine sample for urinalysis
- Review of all inclusion and exclusion criteria

Subjects meeting all of the inclusion criteria and none of the exclusion criteria will return to the clinic within 28 days after screening for enrollment into the study.

From the time of obtaining informed consent through the first administration of investigational medicinal product, record all serious adverse events (SAEs), as well as any adverse events related to protocol-mandated procedures on the adverse events case report form (eCRF). All other untoward medical occurrences observed during the screening period, including exacerbation or changes in medical history are to be captured on the medical history eCRF. See Section 7 Adverse Events and Toxicity Management for additional details.

6.1.2. Baseline Assessments

Day 1 tests and procedures must be completed prior to enrollment and dosing/dispensing of study drug.

At the Day 1 visit, complete the following:

- Confirm subject eligibility
- Review medical history since screening visit including adverse events and concomitant medications
- Perform symptom-directed PE including VS, body weight, and height
- Collect blood samples for clinical chemistry including Fibrotest, hematology, coagulation, HCV RNA, HBV DNA for subjects HBcAb positive at Screening, IL28B genotyping, PPD
[REDACTED]
- Collect urine sample for pregnancy testing for females of childbearing potential
- Pregnancy prevention counseling, if applicable
- Perform LDV/SOF FDC swallowability (only if not previously completed at screening). Observe the subject taking the first dose of study drug (with or without food) and record the time of first dose
- Dispense study drug(s) as directed by IWRS

- Instruct the subject on the packaging, storage and administration of study drug
- Subjects will be administered a dosing diary with instructions.

6.2. Treatment Assessments (\pm 3 days)

Treatment procedures/assessments are to be completed at the end of Weeks 1, 4, 8, and 12, and ESDD as applicable, for all subjects as outlined in [Appendix 2](#).

At all visits:

- Perform symptom-directed PE and VS measurement
- Assess adverse events and concomitant medications since previous visit
- Collect blood samples for HCV RNA measurement **PPD**
- Assess study drug accountability
 - Dispense study medication at Weeks 4 and 8
- Review subject dosing diary

At Weeks 4, 8, and 12, and ESDD if applicable:

- Obtain height and body weight
- Collect blood samples for clinical chemistry and hematology
- Collect blood samples for HBV DNA only in subjects HBcAb positive at Screening
- Collect urine sample for pregnancy testing (females of childbearing potential)

At Weeks 4 and 12, and ESDD if applicable:

PPD

At Week 12 or ESDD:

- Pregnancy prevention counseling, if applicable
- Collect blood samples for Fibrotest and coagulation
- APRI Calculation

6.3. Post-treatment Assessments (\pm 5 days)

All subjects will complete the Post-Treatment Week 4, 12 and 24 visits, regardless of treatment duration.

Assessments at the Post-Treatment Week 4 visit include:

- Obtain height and body weight
- Symptom directed PE and VS
- Adverse events and concomitant medications
- Blood samples for clinical chemistry and hematology including APRI calculation, HCV RNA, HBV DNA only in subjects HBVAb positive at Screening, PPD
- Urine sample for pregnancy testing (females of childbearing potential)
- Pregnancy prevention counseling, if applicable

Assessments at the Post-Treatment Week 12 and 24 visit include:

- Collect any serious adverse events
- Obtain height and body weight
- For those who achieved SVR at the preceding visit (ie, achieved SVR4 or SVR12): Collect blood samples for HCV RNA PPD
- Collect blood samples for Fibrotest PPD
- Perform Fibroscan

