Study Procedures/ Frequency:	
Screening assessments will be completed within 28 days of the Baseline/Day 1 visit.
 
All subjects will complete the following study visits: Screening, Baseline/Day 1, on-treatment visits at the end of Weeks 1, 4, 8, and 12. All subjects will complete the post treatment Weeks 4, 12 and 24 visits.
 
Screening assessments will include physical examination, medical history, body height and weight, vital signs, adverse events related to screening procedures, concomitant medications, safety laboratory tests (including hematology, chemistry, and coagulation), HCV RNA, HCV genotype, serology (HIV antibody, HAV antibody, HCV antibody, hepatitis B surface antigen [HBsAg], hepatitis B surface antibody [HBsAb], hepatitis B core antibody [HBcAb]), assessment of the presence or absence of cirrhosis and fibrosis stage, serum β-hCG (females of child bearing potential only), urinalysis, and LDV/SOF swallowability assessment (may be done up until Day 1). Fibrosis will be assessed via Fibrotest,[®] APRI, and Fibroscan; liver biopsy may be performed if necessary.
 
Baseline/Day 1 assessments include medical history and host IL28B genotyping. Additional Baseline/Day 1 and on-treatment assessments include adverse events (AEs), concomitant medications, study medication pill count, physical examination, height, weight, vital signs, laboratory tests for safety and fibrosis assessments (by Fibrotest at Day 1, Week 12, and ESDD as applicable and APRI at Week 12 and ESDD as applicable), HCV RNA, HBV DNA for subjects HBcAb positive at Screening, PPD pregnancy prevention counseling, and urine pregnancy tests (females of child bearing potential only).

Post-treatment assessments include AEs, concomitant medications, vital signs and physical examination (at 4 weeks post treatment), safety laboratory tests, HCV RNA, HBV DNA for subjects HBcAb positive at Screening, fibrosis assessments (by Fibrotest and Fibroscan at 12 and 24 weeks post treatment, by APRI at Post Treatment Week 4), PPD pregnancy prevention counseling (if applicable), and urine pregnancy tests (females of child bearing potential only).

PPD

Test Product, Dose, and Mode of Administration:

LDV/SOF is manufactured as a FDC tablet, consisting of 90 mg LDV and 400 mg SOF, for oral administration. Subjects will take 1 tablet daily with or without food.

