6.7. Procedures and Specifications

6.7.1. Clinical Laboratory Analytes

- Hematology: Hematocrit, hemoglobin (Hb), platelet count, red blood cell count (RBC), white blood cell count (WBC) with differential (absolute and percentage) including lymphocytes, monocytes, neutrophils, eosinophils, basophils, reticulocyte count and MCV.
- Coagulation: INR, prothrombin time (PT), activated partial thromboplastin time (APTT).
- Chemistry: Alanine aminotransferase (ALT/SGPT), aspartate aminotransferase (AST/SGOT), albumin, alkaline phosphatase, creatinine, total bilirubin (reflex to direct bilirubin), glucose (non-fasting), potassium, sodium; gamma-glutamyl transferase (GGT)
- Fibrotest
- APRI
- Virological Tests: Serologies for HCV, HBV (HBsAg, HBsAb, HBcAb), HAV, and HIV. HCV RNA will be measured using the COBAS® AmpliPrep/COBAS® TaqMan® HCV Quantitative Test, version 2.0. HCV genotype and subtype will be determined using the Siemens VERSANT® HCV Genotype INNO-LiPA 2.0 Assay. HBV DNA testing will be performed only in subjects HBcAb positive at Screening. Alternate assays may be used if the above assays are not available or are not definitive.

- IL28B genotype will be determined by polymerase chain reaction (PCR) amplification of the SNP, rs12979860. Alternate assays may be used if this assay is not available.
- Pregnancy Tests: Serum β -hCG or urine β -hCG (if positive, requires immediate confirmation with serum β -hCG).

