Appendix Table 2. Post-Treatment Study Visits

	4 Weeks Post-Treatment (±5 days)	12 Weeks Post-Treatment ^a (±5 days)	24 Weeks Post-Treatment (±5 days)
Clinical Assessments			
Symptom-directed PE	X		
Height and Weight	X	X	X
Vital Signs	X		
AEs	X	X ^a	X ^a
Concomitant Medications	X		
Fibrosis assessment ^b		X	X
Pregnancy prevention counseling ^c	X		
Laboratory Assessments			
Hematology and Blood Chemistry	X		X
APRI Calculation	X		
HCV RNA	X	X	X
HBV DNA ^d	X	X	X
PPD			
Urine Pregnancy Test ^f	X		

a All SAEs, including deaths, regardless of cause or relationship, must be reported after patient signs the informed consent through the end of the study

b Fibroscan and Fibrotest

c If applicable

d HBV DNA testing done only when subjects are HBcAb positive at Screening

e [Redacted]

f Females of childbearing potential

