3.7.2. Analysis Windows

Subject visits might not occur on protocol-specified days. Therefore, for the purpose of analysis, observations will be assigned to analysis windows. In general, the baseline value will be the last nonmissing value on or prior to the first dose date of study drug.

Safety laboratory data, HCV RNA, vital signs, height and weight, FibroScan, and Fibrotest, collected up to the last dose date + 3 days are considered to be on-treatment data. The analysis windows for on-treatment HCV RNA, vital signs, height and weight, and safety laboratory data are provided in [Table 3-1](#).

Table 3-1. Analysis Windows for On-treatment HCV RNA, Vital Signs, Height and Weight, Fibrotest ^a, and Safety Laboratory Data

Nominal Visit	Nominal Day	Lower Limit	Upper Limit
Baseline	1	(none)	1
Week 1	7	2	11
Week 4	28	12	42
Week 8	56	43	70
Week 12	84	71	≥85

^a Analysis windows for coagulation parameters and Fibrotest are only defined for Baseline and Week 12.

^b FibroScan is collected at screening, posttreatment week 12 and posttreatment week 24.

Safety laboratory data, HCV RNA, vital signs, height and weight, FibroScan, and Fibrotest, collected after the last dose date + 3 days will be assigned to the posttreatment follow-up (FU) visits. Visit windows will be calculated from the last dose date (ie, FU Day = collection date minus the last dose date) as shown in [Table 3-2](#).

Table 3-2. Analysis Windows for Posttreatment HCV RNA, Vital Sign, Height and Weight, FibroScan, Fibrotest, and Safety Laboratory Data

Nominal FU ^a Visit	HCV RNA, Height and Weight, FibroScan and Fibrotest			Vital Signs and Safety Laboratory Data ^b		
	Nominal FU Day	Lower Limit	Upper Limit	Nominal FU Day	Lower Limit	Upper Limit
FU-4 ^c	28	21	69	28	4	30
FU-12	84	70	146	NA	NA	NA
FU-24	168	147	210	NA	NA	NA

^a FU-x visit = posttreatment Week-x follow-up visit.

^b Vital signs and safety labs will only be summarized for the FU-4 visit (up to 30 days after last dose).

^c Doesn't apply to FibroScan and Fibrotest.

3.7.3. Selection of Data in the Event of Multiple Records in an Analysis Window

Depending on the statistical analysis method, single values may be required for each analysis window. For example, change from baseline by visit usually requires a single value, whereas a time-to-event analysis would not require 1 value per analysis window.

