7.2. Laboratory Evaluations

Laboratory data collected during the study will be analyzed and summarized using both quantitative and qualitative methods. Summaries of laboratory data will be provided for the Safety Analysis Set and will include data collected up to the last dose of study drug plus 30 days for subjects who have permanently discontinued study drug or all available data at the time of the database snapshot for subjects those who were ongoing at the time of an interim analysis. The analysis will be based on values reported in conventional units. When values are below the limit of quantitation, they will be listed as such, and the closest imputed value will be used for the purpose of calculating summary statistics. For example, if “< 0.2” was recorded, a value of 0.1 will be used for the purpose of calculating summary statistics; if “< 0.1” was recorded, a value of 0.09 will be used for the purpose of calculating summary statistics. Hemolyzed test results will not be included in the analysis, but they will be listed in by-subject laboratory listings.

A by-subject listing for laboratory test results will be provided by subject ID number and visit in chronological order for hematology, serum chemistry, and urinalysis separately. Values falling outside of the relevant reference range and/or having a severity grade of 1 or

higher on the Gilead Grading Scale for Severity of Adverse Events and Laboratory Abnormalities will be flagged in the data listings, as appropriate.

No inferential statistics will be generated.

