7.5. Other Safety Measures

A data listing for cirrhosis determination will be provided for all subjects at screening.

A data listing will be provided for subjects who become pregnant during the study.

No additional safety measures are specified in the protocol.

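### Do the wording of Protocol 6.3 on post-treatment HBV DNA and the SAP's silence on that test call for a change to the plan?

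*Protocol*

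**What the plan says.** **Protocol, text.** Section 6.3 names HBV DNA in its post-treatment Week 4 list, as "HBV DNA only in subjects HBVAb positive at Screening". Its Week 12 and 24 list shows serious adverse events, height and weight, HCV RNA, Fibrotest and Fibroscan. The HCV RNA and Fibrotest items both end in redacted text.

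**Protocol, schedule.** Appendix Table 2 marks HBV DNA at post-treatment Weeks 4, 12 and 24, with the footnote "HBV DNA testing done only when subjects are HBcAb positive at Screening". The synopsis puts the test among the post-treatment assessments without limiting it to one visit: "HCV RNA, HBV DNA for subjects HBcAb positive at Screening, fibrosis assessments". Section 6.7.1, on laboratory analytes, says "HBV DNA testing will be performed only in subjects HBcAb positive at Screening".

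**SAP.** Appendix 1 repeats the protocol schedule. Nowhere else in the visible text is HBV DNA named. Section 7.2 promises listings by "visit in chronological order for hematology, serum chemistry, and urinalysis separately". A footnote to Table 3-2 restricts summaries of vital signs and safety laboratory data to the Week 4 follow-up visit, up to 30 days after the last dose. Section 7.5 closes with "No additional safety measures are specified in the protocol".

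**The concern.** Two descriptions of one procedure should agree, and here they do not. A site working from 6.3 alone would draw HBV DNA once after treatment instead of three times. It would also meet a marker name that matches neither of the two hepatitis B antibodies tested at screening (HBsAb and HBcAb) and that is missing from the glossary.

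The SAP then appears to leave the results without a home: no named window, no summary, no named listing panel. If the values were handled as safety laboratory data, the follow-up window would shut out the two later visits.

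Safety is a primary objective. Only HBsAg-positive subjects are excluded for hepatitis B, so HBcAb-positive subjects can enroll. If late samples were missed, or were drawn and never shown, part of the planned safety follow-up would be lost.

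**Working it through.** No sample size, power or interval figure depends on this point. The check is a comparison of passages, a count of visits and a check of days.

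**1. Scheduled HBV DNA time points, subject completing treatment**

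| Source | Time points | Count |
|---|---|---|
| Appendix Tables 1 and 2 | Day 1; Weeks 4, 8, 12; post-treatment Weeks 4, 12, 24 | 7 |
| Visible text of 6.1.2, 6.2, 6.3 | Day 1; Weeks 4, 8, 12; post-treatment Week 4 | 5 |

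Difference: 7 − 5 = 2, namely post-treatment Weeks 12 and 24.

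**2. Does the text contradict the table, or only say less?** It says less. The Week 12 and 24 list is introduced as what the visit includes, and nothing states that HBV DNA is not drawn. The same list also leaves out the hematology and chemistry that Appendix Table 2 marks at Week 24, so it is abbreviated in general. Section 6 opens with "The study procedures to be conducted for each subject enrolled in the study are presented in tabular form in" Appendix 2, and Section 6.5 points to 6.3 and Appendix 2 together for the post-treatment visits. With two blood-sample items ending in redactions, an omission is not even proven.

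**3. Which marker?** HBcAb is used in the synopsis, 6.1.2, 6.2, 6.7.1, Protocol Appendix Tables 1 and 2, and the SAP copies of both tables: eight places against one. Section 6.7.1 gives it as a general rule for the test.

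**4. The SAP window.** Protocol visits are allowed ±5 days; SAP Table 3-2 puts safety laboratory data at follow-up days 4 to 30.

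- Week 4: 28 ± 5 gives days 23–33; days 31, 32 and 33 fall outside, 3 of 11.
- Week 12: 84 ± 5 gives days 79–89; 11 of 11 outside.
- Week 24: 168 ± 5 gives days 163–173; 11 of 11 outside.

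The arithmetic is right, but the window governs summaries. Protocol 8.6.3 promises summaries of selected laboratory data only, the SAP's choice in 7.2.1 does not include HBV DNA, and the grading scale in Protocol Appendix 3 has no HBV DNA row. There is no HBV DNA summary to lose values from. The 30-day limit itself comes from Protocol 8.2.1.2, 8.6 and 8.6.3, and the Week 4 effect applies to every safety laboratory test.

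**5. Are the values shown?** Protocol 8.2 has all individual data listed as measured, and SAP Section 3 lists collected data by subject unless stated otherwise. SAP 7.2 names three panels but does not confine listings to them. The largest possible scheduled listing is 19 × 7 = 133 values, of which 19 × 2 = 38 come from Weeks 12 and 24, if all 19 enrolled subjects were HBcAb positive and completed every visit. The smallest is 0.

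**6. SAP 7.5.** Protocol 6.7.1 places HBV DNA among the laboratory analytes, and Protocol 8.6.4, on other safety evaluations, names only vital signs. The SAP sentence agrees with that classification.

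**The case for a change.** The best case for a change has four parts.

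First, HBV DNA is left unredacted wherever it appears, including the Week 4 item of the same section, so it is unlikely that the hidden text at Weeks 12 and 24 contains it. That is fair, and the text is probably incomplete. Incomplete is still not contrary, because Appendix Table 2 is explicit.

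Second, no sentence says whether text or table governs, so it could be disputed whether a missing Week 12 or 24 sample is a deviation. In practice, a sample marked in the schedule and not ruled out elsewhere is a scheduled sample. A missing one would show as a gap in the listing.

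Third, a test scheduled at seven visits deserves a named output, and a count of subjects moving from not detected to detected would be easy to read. This is a reasonable preference. But the visible documents state neither a purpose for the test nor an HBV DNA assay or detection limit, so the count would rest on definitions the plan does not contain. With at most 19 subjects, a reader can see any such change in the listing itself.

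Fourth, aligning 6.3 with the table costs almost nothing. True, but enrollment has ended at a single site, and the wording changes no analysis.

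What stands is that 6.3 is loosely worded and its marker name is a slip.

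**Conclusion.** No change to the plan follows. The difference of two time points and the stray marker name are clerical: read as a whole, the protocol gives one schedule and one selection rule. The absence of a named HBV DNA output is a detail that the general listing rules already cover. The late values fall outside the 30-day safety summaries by the protocol's own rule, and no planned summary of HBV DNA exists for that rule to truncate. The SVR12 estimate, its interval and the planned safety tables are unaffected.

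This rests on three assumptions: that the site works from Appendix 2 as Section 6 directs, that the listing rules in Protocol 8.2 and SAP Section 3 are applied to virology results, and that the redacted exploratory sections of the SAP (6.3.1 and 6.3.2), which cannot be checked, do not say otherwise. Between 0 and 19 subjects are concerned. Whether the HBV DNA schedule is clinically right is not judged here.
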